4.6.3.2. Laboratory and Adverse Event for Hepatic Safety

Hepatic labs include:

- alanine aminotransferase (ALT),
- aspartate aminotransferase (AST),
- total bilirubin (TBL),
- direct bilirubin (DBL),
- serum alkaline phosphatase (ALP), and

- gamma-glutamyltransferase (GGT).

When criteria are met for hepatic evaluations, investigators will conduct close monitoring of hepatic symptoms and liver tests, perform a comprehensive evaluation for alternative causes of abnormal liver tests, and complete follow-up hepatic safety CRFs.

The table below lists summary TFLs for the analysis of hepatic laboratory data.

Analysis	Details
Abnormal postbaseline categories – hepatic safety parameters	
ALT: The number and percentage of participants with a measurement greater than or equal to 1 time (1\times), 3 times (3\times), 5 times (5\times), 10 times (10\times), and 20 times (20\times) the performing laboratory ULN during the postbaseline period will be summarized for all participants with a postbaseline value.
 
AST: The number and percentage of participants with a measurement greater than or equal to 1 time (1\times), 3 times (3\times), 5 times (5\times), 10 times (10\times), and 20 times (20\times) the performing laboratory ULN during the postbaseline period will be summarized for all participants with a postbaseline value.
 
ALP: The number and percentage of participants with a measurement greater than or equal to 2 times (2\times) and 3 times (3\times) the performing laboratory ULN during the postbaseline period will be summarized for all participants with a postbaseline value.
 
TBL: The number and percentage of participants with a measurement greater than or equal to 2 times (2\times), 5 times (5\times), and 8 times (8\times) the performing laboratory ULN during the postbaseline period will be summarized for all participants with a postbaseline value.
 
DBL: The number and percentage of participants with a measurement greater than or equal to 2 times (2\times) and 5 times (5\times) the performing laboratory ULN during the postbaseline period will be summarized for all participants with a postbaseline value.
 
GGT: The number and percentage of participants with a measurement greater than or equal to 2 times (2\times) the performing laboratory ULN during the postbaseline period will be summarized for all participants with a postbaseline value.

Treatment-emergent potentially drug-related hepatic disorders	
Potentially drug-related hepatic disorders are defined using a custom query based on the following SMQs:
 
 • Broad and narrow terms in the Liver-related investigations, signs and symptoms SMQ (20000008); • Broad and narrow terms in the Cholestasis and jaundice of hepatic origin SMQ (20000009); • Broad and narrow terms in the Hepatitis non-infections SMQ (20000010); • Broad and narrow terms in the Hepatic failure, fibrosis and cirrhosis and other liver damage SMQ (20000013); and • Narrow terms in the Liver-related coagulation and bleeding disturbances SMQ (20000015).

Analysis	Details
	
These SMQs are a subset of the sub-SMQs comprising the full Hepatic Disorders SMQ. Only the sub-SMQs considered applicable to capturing potentially drug-related hepatic disorders are included.
 
The percentage of study participants with at least one of any of the MedDRA preferred terms from any of the above SMQs will be summarized in addition to the percentages for each MedDRA preferred term.

Hepatocellular drug-induced liver injury screening plot (TBL vs ALT or AST)	
Each participant's data is plotted based on their maximum postbaseline TBL (y-axis) and transaminase (ALT or AST, whichever is higher), regardless of the time between the 2 maximum values. Lines represent TBL and transaminase cutoffs of $2 \times$ ULN and $3 \times$ ULN, respectively. A potential Hy's law case is circled and is defined as having a maximum postbaseline TBL equal to or exceeding $2 \times$ ULN within 30 days after maximum postbaseline ALT or AST equal to or exceeding $3 \times$ ULN, without cholestasis (defined as ALP less than $2 \times$ ULN).

Hepatocellular drug-induced liver injury screening table	
The percentages of study participants falling in each of the 3 relevant quadrants of the plot (right upper, left upper, right lower) will be summarized in a table.

Cholestatic drug-induced liver injury screening plot (TBL vs ALP)	
Each participant's data is plotted based on their maximum postbaseline TBL (y-axis) and ALP (x-axis), regardless of the time between the 2 maximum values. Lines represent TBL and ALP cutoffs of $2 \times$ ULN and $3 \times$ ULN, respectively. A potential cholestatic liver injury case is circled and is defined as having a maximum postbaseline TBL equal to or exceeding $2 \times$ ULN within 30 days after maximum postbaseline ALP equal to or exceeding $3 \times$ ULN.

Cholestatic drug-induced liver injury screening table	
The percentages of study participants falling in each of the 3 relevant quadrants of the plot (right upper, left upper, right lower) will be summarized in a table.

List of Participants with potential hepatocellular drug-induced liver injury	
Includes participants falling in the right upper quadrant in the Hepatocellular Drug-Induced Liver Injury Screening plot.

List of Participants with potential cholestatic drug-induced liver injury	
Includes participants falling in the right upper quadrant in the Cholestatic Drug-Induced Liver Injury Screening plot.

Abbreviations: ALP = alkaline phosphatase; ALT = alanine aminotransferase; AST = aspartate aminotransferase; CRF = case report form; DBL = direct bilirubin; GGT = gamma-glutamyl transferase; MedDRA = Medical Dictionary for Regulatory Activities; SMQ = Standardized MedDRA Query; TBL = total bilirubin; ULN = upper limit of normal.

Planned and unplanned measurements will be included. The measurements do not need to be taken at the same blood draw.

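### A later, higher transaminase peak with normal bilirubin removes the potential Hy's law circle from a participant who met every threshold on an earlier draw

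*SAP*

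**What the plan says.** SAP 4.6.3.2 gives each participant one point on the hepatocellular plot: maximum postbaseline TBL against the higher of maximum ALT or AST, "regardless of the time between the 2 maximum values". Separately, points that count as potential Hy's law cases are circled, on three conditions. The bilirubin condition is "having a maximum postbaseline TBL equal to or exceeding $2", in multiples of ULN. The timing clause is "within 30 days after maximum postbaseline ALT or AST equal to or exceeding"; its transaminase threshold is three times ULN. The last condition is "without cholestasis (defined as ALP less than", where the ALP limit is twice ULN. No date or draw is attached to the ALP condition.

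The plot has a companion table: "The percentages of study participants falling in each of the 3 relevant quadrants of the plot (right upper, left upper, right lower"). A listing takes everyone in the right upper quadrant. Neither depends on the circle. The cholestatic plot repeats the construction, with maximum TBL within 30 days after maximum ALP of at least 3 × ULN.

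The section includes planned and unplanned measurements and does not require them to come from the same draw. Under the SAP 4.1 table, the postbaseline period for elevated laboratory values runs from after the first dose day to the last study visit, follow-up included.

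**The concern.** A screening flag for potential Hy's law should depend on whether raised bilirubin accompanied or soon followed raised transaminases. This flag depends on when each participant's highest values fell, over about 57 weeks. Worse liver data can therefore cancel it: a second, higher ALT rise moves the transaminase maximum away from the episode that qualified.

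Such sequences are plausible here. Exclusion criterion 20 admits participants with non-alcoholic fatty liver disease, ALT or AST up to 3 × ULN, and previously diagnosed Gilbert's disease with raised bilirubin. Protocol 7.1 keeps participants in the study after they stop study intervention, so an off-treatment peak can displace an on-treatment episode. Protocol 7.1.1 treats ALT or AST above 3 × ULN with TBL above 2 × ULN as an occurrence, not through maxima. A participant who met that criterion could therefore be uncircled on the SAP's plot.

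What is at stake is how participants inside the quadrant are told apart. The circle is the only hepatic output in SAP 4.6.3.2 that applies both timing and the cholestasis condition.

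**Working it through.** The documents state no figure for this rule, so the check applies its text to constructed records.

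**Inputs.** Thresholds and the 30-day window come from SAP 4.6.3.2. Laboratory values are assumed, in multiples of ULN, with ALP at 1 throughout. A same-day pair is counted as inside the window, because the section allows but does not require values from one draw.

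**Rules compared.**
- *Literal*: overall maximum TBL ≥ 2, dated 0 to 30 days after the overall maximum transaminase ≥ 3.
- *Window*: highest TBL in the 30 days from the maximum transaminase is ≥ 2.
- *Any-pair*: any TBL ≥ 2 dated 0 to 30 days after any ALT or AST ≥ 3.

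The lag is the day of maximum TBL minus the day of maximum transaminase. For A, B and C, AST is assumed not to have its own qualifying peak on a different draw from ALT.

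| Record | Draws | Lag (days) | Literal | Window | Any-pair |
|---|---|---|---|---|---|
| Base | Day 84: ALT 5, AST 4, TBL 2.5; then normal | 0 | circled | circled | circled |
| A | Week 12: ALT 4, TBL 2.5; Week 26: ALT 6, TBL 1 | (12 − 26) × 7 = −98 | no | no | circled |
| A, shorter gap | Base, plus day 98: ALT 6, AST 5, TBL 0.8 | 84 − 98 = −14 | no | no | circled |
| A, ALT only | Base, plus day 182: ALT 6, AST 1, TBL 0.8 | −98 using the higher enzyme; 0 using AST alone | no; circled if AST is tested separately | no; circled if AST is tested separately | circled |
| B | Day 84: ALT 5, TBL 2.2; day 87: ALT 5.5, TBL 2.0 | 84 − 87 = −3 | no | circled | circled |
| C | Day 84: ALT 4, TBL 2.1; day 364: TBL 2.4, ALT normal | 364 − 84 = 280 | no | circled | circled |
| Later TBL, 20 days | Base, plus day 104: TBL 3.0, enzymes normal | 104 − 84 = 20 | circled | circled | circled |

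Every record has maximum transaminase ≥ 3 and maximum TBL ≥ 2. All seven therefore plot in the right upper quadrant, enter its percentage and are listed.

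**Sampling.** Postbaseline chemistry is scheduled at Weeks 12, 26, 52 and 57, and at early discontinuation. Nominal gaps are (26 − 12) × 7 = 98, (52 − 26) × 7 = 182 and (57 − 52) × 7 = 35 days. The visit windows are ±3 days at Week 52 and ±7 days at Week 57, so the last gap can shrink to 35 − 3 − 7 = 25 days. Protocol 8.2.5 adds repeats at 48 to 72 hours, then 1 to 3 times weekly if an abnormality persists or worsens. The two maxima can therefore fall on different draws in either order, while the rule accepts only bilirubin on or after the transaminase date.

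**The case against.** The strongest reply is that the circle is only an annotation. The SAP plans no count of circled participants. The tabulated and listed outputs ignore timing and keep every record above. Individual cases are handled outside the plot: records like these meet a liver criterion in Protocol 7.1.1. With baseline TBL below 1.5 × ULN and no Gilbert's syndrome, TBL of at least 2 × ULN also calls for repeat testing, comprehensive evaluation and the hepatic safety CRF under Protocol 8.2.5. This stands, and it limits the point.

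It rules out three stronger readings that a reader might infer.
- That the trial could report no potential case, or lose one. It could not: the quadrant table and listing still show the participant.
- That any later isolated peak removes the circle. A bilirubin peak 20 days later leaves it in place. Records B and C lose it only on the literal reading. A later rise in ALT alone leaves it in place if AST is tested separately and peaked with the qualifying draw.
- That scheduled draws can produce a circle only when both maxima fall on the same draw. The visit windows allow a 25-day gap between the last two.

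The reply does not rescue Record A, which fails on both readings. The quadrant table and listing also cannot replace the circle, because they apply neither the 30-day window nor the ALP condition.

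**Conclusion.** The point holds in a limited form. As written, the rule leaves uncircled a participant who met all thresholds on one draw if a higher transaminase peak with normal bilirubin follows, even 14 days later. That result does not depend on how the bilirubin maximum is read. It does assume that AST has no separate maximum on the qualifying draw, or that the higher of the two enzymes is used.

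On the literal reading only, the circle is also lost when the TBL maximum falls more than 30 days after the transaminase maximum, or a few days before it. That two fair readings give different answers is itself a reason to tighten the wording. The cholestatic flag shares the maximum-to-maximum form.

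The consequence is misidentification within a display, not loss of a participant. The documents give no rates of liver-test elevation, so the number affected cannot be computed. This is a worthwhile clarification, not a threat to the liver-safety evaluation.

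**What to change.** In SAP 4.6.3.2, define the potential Hy's law flag as any postbaseline TBL of at least 2 × ULN on the same day as, or within 30 days after, any postbaseline ALT or AST of at least 3 × ULN. Keep the ALP below 2 × ULN condition and state which ALP value it applies to, for example the one on the qualifying transaminase draw. Reword the parenthesis so that ALP below 2 × ULN clearly describes the absence of cholestasis.

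Use the same any-pair form for the cholestatic flag, with ALP of at least 3 × ULN. Keep the maxima as plot coordinates only, so the quadrant tables and listings do not change.

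The cost is a wording change and a small programming change, with no new data. A few more participants may be circled and need case review.

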4.6.3.3. Clinical Laboratory Evaluations

For the following selected laboratory measures:

- Liver enzyme tests: ALT, ALP, AST, GGT, DBL and Total Bilirubin, and
- Lipid measures: Triglycerides, total cholesterol, LDL-C, and HDL-C (results from fasting samples).

MMRM model (as described in Section 4.6) will be used for the observed values, change from baseline and percentage change from baseline, for which log-transformation will be applied. Geometric LS means will be provided. Analyses will be provided in both international units (SI) and conventional units (CN) if they are different.

Box plots with descriptive statistics for the observed values and change from baseline will be provided by treatment group and visit.

For other laboratory measures, descriptive summaries will be provided for the observed values and change from baseline by treatment group and visit.

The percentages of patients with elevated or low values meeting specified levels (see Appendix 11, Section 6.11) at any time postbaseline (including scheduled and unscheduled measurements) will be summarized and compared between treatment groups using risk difference and 95% confidence interval.

A listing of abnormal laboratory analytes collected quantitatively (high or low during postbaseline using Level 2 definitions in Appendix 11, Section 6.11) and qualitatively (abnormal during postbaseline) will be provided, including participant identification, treatment group, laboratory sample collection day (that is, days from start of study drug), analyte name, abnormal result, and reference low or high limits (Level 2 cut-off value).

Scatter plots of maximum-by-maximum measurements and minimum-by-minimum measurements will not be created a-priori. They may be created if warranted after review of the planned tables and figures, using Figures 6.3 and 6.4 from the Analysis and Displays for Labs white paper (PHUSE 2022) as the model. ADaM datasets will include variables to enable the creation of scatter plots for use in either an interactive tool or for ad-hoc figures.

4.6.3.4. Vital Signs and Physical Characteristics

The planned summaries are provided in the Table below. The measurements analyzed for vital signs and physical characteristics include systolic BP, diastolic BP, pulse, weight, and BMI.

Analysis Type	Analysis Details
Observed values change by visit	
 • Includes all participants in the safety population who have both a baseline and at least 1 postbaseline observation • MMRM model (as described in Section 4.6) will be used. 
See also: Table 6.2 from the Analyses and Displays for Labs white paper (PHUSE 2022)

Summary by category	
 • Definitions provided in Tables 31-33 from FDA's September 2022 Standard Safety Tables and Figures document will be used for the numerator. 
 ○ Systolic BP (mm Hg): 
 ▪ Low: Level 1: <90 ▪ High: Level 1: ≥ 90, Level 2: ≥ 120,

Analysis Type	Analysis Details
	
Level 3: ≥ 140, Level 4: ≥ 160, Level 5: ≥ 180
 
 ○ Diastolic BP (mm Hg): 
 ■ Low: Level 1: < 60 ■ High: Level 1: ≥ 60, Level 2: ≥ 90, Level 3: ≥ 110, Level 4: ≥ 120 ● Includes participants with at least one postbaseline measurement... ● Statistical comparisons (using methods described in Section 4.6) will be included.
Participants meeting CTCAE grade changes in weight	
For weight, cutoffs informed by CTCAE version 5 (Grades 1-3) will be used:
 
 ○ (Loss) decrease: Level 1: $\geq 5\%$, Level 2: $\geq 10\%$, Level 3: $\geq 20\%$ ○ (Gain) increase: Level 1: $\geq 5\%$, Level 2: $\geq 10\%$, Level 3: $\geq 20\%$ 
Includes participants with both a baseline and at least 1 postbaseline observation. Statistical comparisons (using methods described in Section 4.6) will be included.

Abbreviations: BP = blood pressure; CTCAE = Common Terminology Criteria for Adverse Events; FDA = Food and Drug Administration; MMRM = mixed-model repeated measures.

Scatter plots to support vital sign evaluations

Scatter plots of maximum-by-maximum measurements and minimum-by-minimum measurements will not be created a-priori. They may be created if warranted after review of the planned tables and figures, using Figures 6.3 and 6.4 from the Analysis and Displays for Labs white paper (PHUSE 2022) as the model. ADaM datasets will include variables to enable the creation of scatter plots for use in either an interactive tool or for ad-hoc figures.

4.6.4. Device Product Complaints

A summary of all product complaints, inclusive of device product complaints that lead to an AE and/or SAE will be included by category. Additional summaries may be provided as deemed appropriate.

4.7. Other Analyses

4.7.1. Immunogenicity

A participant is evaluable for TE ADA if the participant has a nonmissing baseline ADA result, and at least 1 nonmissing postbaseline ADA result.

A participant who is evaluable for TE ADA is TE ADA+ if either of the following holds:

- Treatment-induced ADA: the participant has baseline status of ADA Not Present and at least 1 postbaseline status of ADA Present with titer $\geq 1:40$, which is $2 \times$ minimum required dilution (MRD) of the ADA assay (MRD=1:20).
- Treatment-boosted ADA: the participant has baseline status of ADA Present and at least 1 postbaseline status of ADA Present with the titer being ≥ 2 dilutions (4-fold) of the baseline titer. That is, the participant has baseline (B) status of ADA Present, with titer 1:B, and at least 1 postbaseline (P) status of ADA Present, with titer 1:P and $P/B \geq 4$.

Refer to PSAP for all definitions and additional details for immunogenicity.

All analyses will be based on all evaluable TE ADA participants. The baseline ADA status will be summarized by treatment group. The number and percentage of participants who are TE ADA+ will be summarized by treatment group. The summary will include the number and percentage of participants with treatment-induced ADA and treatment boosted ADA. A summary of titer values will be provided for participants who are TE ADA positive. This analysis will be performed for the following periods:

- The treatment period up to treatment discontinuation, and
- The entire postbaseline period, including safety follow-up.

A number of additional analyses of the immunogenicity data from this study will be presented in an integrated summary document, alongside data from other studies. The analyses to be performed are described in the PSAP.

4.7.2. Subgroup analyses

The interaction effects will be evaluated using a significance level of 0.05, unadjusted. Subgroup analyses will be conducted as defined in this section. Additional subgroup analysis may also be performed as appropriate.

4.7.2.1. Subgroup analyses for GLP-1 RA use at randomization

The following outcomes will be included in the subgroup analyses for GLP-1 RA use at randomization:

- rate of participant-reported Level 1 hypoglycemia events during Weeks 0 to 26, Weeks 26 to 52, and Weeks 0 to 52;
- rate of participant-reported composite of Level 2 and 3 hypoglycemia events during Weeks 0 to 26, Weeks 26 to 52, and Weeks 0 to 52;
- change from baseline to Week 26 and Week 52 in body weight;
- insulin dose at Week 26 and Week 52; and
- measurements collected during CGM sessions collected prior to Weeks 12, 26, and 52 of:
 - time in hypoglycemia with glucose <70 mg/dL (3.9 mmol/L),
 - time in hypoglycemia with glucose <54 mg/dL (3.0 mmol/L),
 - time in hyperglycemia defined as glucose >180 mg/dL (10.0 mmol/L), and
 - time in glucose range between 70 and 180 mg/dL (3.9 and 10.0 mmol/L), inclusive.

The hypoglycemia rates will be analyzed using a negative binomial regression including the same independent variables for hypoglycemia event analyses (see Section 4.6.3.1) plus 2-way interaction of GLP-1 RA use at randomization and treatment.

Analyses for change from baseline in body weight will be performed by the MMRM model using the same independent variables as described in Section 4.6.3.4 plus GLP-1 RA use at randomization, 2-way interaction of GLP-1 RA use at randomization and visit, and 3-way interaction of treatment, visit and GLP-1 RA use at randomization.

Analyses for insulin dose and CGM parameters will be performed by the MMRM model using the same independent variables as described in Section 4.4.2.1 plus 2-way interaction of GLP-1 RA use at randomization and visit, and 3-way interaction of treatment, visit and GLP-1 RA use at randomization.

Separate analysis without the terms related with the subgroup will be performed for each subpopulation.

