9.3.7. Subgroup Analyses

The following outcomes will be analyzed by the subgroups of GLP-1 RA use at randomization:

- rate of Level 1 hypoglycemia events during Weeks 0 to 26, Weeks 26 to 52, and Weeks 0 to 52
- rate of composite of Level 2 and 3 hypoglycemia events during Weeks 0 to 26, Weeks 26 to 52, and Weeks 0 to 52
- change from baseline to Week 26 and Week 52 in body weight
- insulin dose at Week 26 and Week 52
- measurements collected during CGM sessions collected prior to Weeks 12, 26, and 52 of
 - time in hypoglycemia with glucose <70 mg/dL (3.9 mmol/L)
 - time in hypoglycemia with glucose <54 mg/dL (3.0 mmol/L)
 - time in hyperglycemia defined as glucose >180 mg/dL (10.0 mmol/L), and
 - time in glucose range between 70 and 180 mg/dL (3.9 and 10.0 mmol/L, respectively), inclusive.

The analyses will evaluate whether the treatment impact is different by the subgroups. The models used for these analyses will vary depending on the outcome. Other subgroup analyses may be performed as deemed appropriate.

Details of the modeling will be provided in the SAP.

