by CGM Session during treatment period will also be summarized for LY3209590. Missing data patterns will be summarized at daily, weekly (visit) and CGM session levels.

For CGM parameters, data from participants in China using Libre Freestyle H system will be analyzed separately ([Appendix 6](#) [Section 6.6]).

The analysis of study insulin dose will use an MMRM model on the EAS2 data with treatment, strata (country, GLP-1 RA treatment at randomization, SU use at randomization, and baseline HbA1c stratum [$<8.0\%$, $\geq 8.0\%$]), visit and treatment-by-visit interaction as covariates. The average weekly dose during each visit for individual participants will be used in the analysis. In the LY3209590 group, the average dose of each visit (that is, average of weekly doses since last visit) will be used as the average weekly dose. In the insulin degludec group, the average weekly dose will be calculated by the average daily dose multiplying by 7. The analysis will be repeated for average daily dose in U and daily dose in U/kg. The body weight at the visit will be used to calculate the daily dose in U/kg at the same visit.

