4.6.3. Additional Safety Assessments

4.6.3.1. Hypoglycemic Events

4.6.3.1.1. Participant-Reported Hypoglycemic Events

The following types of hypoglycemia events will be derived in the analysis data sets: documented hypoglycemia as Level 1, Level 2, and Level 3 (severe hypoglycemia) according to definitions based on the American Diabetes Association criteria where:

- Level 1: glucose <70 mg/dL (3.9 mmol/L) and ≥ 54 mg/dL (3.0 mmol/L);
- Level 2: glucose <54 mg/dL (3.0 mmol/L); and
- Level 3: severe hypoglycemia (confirmed by the investigator to be an event that required assistance for treatment).

Level 2 and Level 3 events are considered clinically significant hypoglycemia. Therefore, the analysis on a composite of Level 2 and Level 3 (denoted as Level 2/3) hypoglycemia will also be conducted.

Hypoglycemia will also be further classified into:

- nocturnal hypoglycemia (occurs between midnight and 0600); and
- non-nocturnal hypoglycemia (occurs between 0600 and midnight).

If a hypoglycemic event is within 60 minutes of another hypoglycemic event, it is considered as a continuation of the previous event. If there are multiple hypoglycemic events within 60 minutes of each other, then all events will be combined into a single event, which has the:

- earliest date time;
- minimum glucose value, if applicable;
- maximum severity (Level 1, 2 or 3);
- combined all symptoms and outcomes; and
- time of nocturnal if any of the events is nocturnal;

of the multiple hypoglycemic events.

The combined event starts from the first record with Level 1, 2 or 3, and ends when there are no more events for at least 60 minutes.

The evaluation of potential persistent-recurrent hypoglycemia events will be through assessment of the clinically significant events confirmed by investigators based on clinical judgment and through events identified by a pre-specified criteria (Section 4.6.2.1.2 and [Appendix 10](#), Section 6.10) using information based on the participant-reported hypoglycemia.

The details of planned analyses are provided in the below table.

Endpoint	Analysis Period	Statistical Method
Event rate of Level 1 hypoglycemia events (events/participant/year): • All documented	Baseline, 0-6, 0-12, 0-26, 0-52, 12-26, 26-52 weeks, post-treatment period	Negative binomial regression with treatment and baseline HbA1c as covariates, log (exposure/365.25 days) as the offset in the model.

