4.7.2.3. Subgroup analyses in hypoglycemia

Subgroup analyses of documented Level 2/3 hypoglycemia, non-nocturnal and nocturnal hypoglycemia rates during 0-52 weeks will be conducted. The subgroups are defined as:

- Baseline HbA1c stratum (<8.0% and \geq 8.0%),
- Region (US and non-US),
- Region (North America, South America, Europe, Asia), and

- SU use at randomization.

Estimated glomerular filtration rate (eGFR) at baseline (<60, 60 - <90, and ≥ 90 mL/min/1.73 m²) The hypoglycemia rates will be analyzed using a negative binomial regression including the same independent variables for hypoglycemia event analyses (see Section 4.6.3.1) plus factors of subgroup, 2-way interaction of subgroup and treatment.

Separate analysis without the terms related with the subgroup will be performed for each subpopulation.

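### The GLP-1 RA interaction model for hypoglycemia rates in SAP 4.7.2.1 has no GLP-1 RA main effect, so the term as written does not test whether the treatment effect differs by GLP-1 RA use

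*SAP*

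**What the plan says.** - **The model.** For the GLP-1 RA subgroup analysis of Level 1 and composite Level 2/3 rates, SAP 4.7.2.1 takes the independent variables of 4.6.3.1 "plus 2-way interaction of GLP-1 RA use at randomization and treatment".
- **The base variables.** For the Level 1 rate, SAP 4.6.3.1.1 specifies "Negative binomial regression with treatment and baseline HbA1c as covariates, log (exposure/365.25 days) as the offset in the model". The Level 2/3 row has the same covariates and offset. Neither contains GLP-1 RA use or any other stratification factor.
- **The purpose.** Protocol 9.3.7: "The analyses will evaluate whether the treatment impact is different by the subgroups". It leaves the modeling to the SAP.
- **The decision rule.** SAP 4.7.2: "The interaction effects will be evaluated using a significance level of 0.05, unadjusted".
- **The neighboring models.** The body-weight model in the same section adds the factor explicitly: "plus GLP-1 RA use at randomization, 2-way interaction of GLP-1 RA use at randomization and visit". The other hypoglycemia subgroup models, in SAP 4.7.2.3, are written "plus factors of subgroup, 2-way interaction of subgroup and treatment", but GLP-1 RA use is not among the subgroups listed there. The insulin dose model inherits GLP-1 RA use from SAP 4.4.2.1, which lists "treatment, strata (country, GLP-1 RA treatment at randomization, SU use at randomization, and baseline HbA1c stratum"; the CGM models inherit it from that section too.

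**The concern.** An interaction between a two-level subgroup and treatment measures a difference in treatment effect only when both main effects are in the model. Here one is missing. Background hypoglycemia rates could well differ between GLP-1 RA users and non-users for reasons unrelated to the randomized insulin. If they do, the term as written picks up that difference and can be reported as treatment-effect heterogeneity. Under one coding it can also miss heterogeneity that is real.

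The comparison by GLP-1 RA use is a stated tertiary objective. GLP-1 RA use is also a stratification factor, planned at about half of the participants. Six tests rely on this model: 2 event types (Level 1, Level 2/3) × 3 periods (Weeks 0–26, 26–52, 0–52).

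**Working it through.** The plan gives no power or event rate for this model, so there is no figure to reproduce. The only number attached to it is the nominal 0.05.

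**Algebra.** Let T = 1 for LY3209590, G = 1 for GLP-1 RA use, H = baseline HbA1c. The full model is

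log(rate) = β0 + β1·T + β2·H + δ·G + θ·T·G

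The stated question is whether θ = 0. With δ·G left out there are two readings:

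1. *Class coding.* The interaction term carries one GLP-1 RA effect per arm: γ0 = δ in the degludec arm and γ1 = δ + θ in the LY3209590 arm. The test of the term has 2 df, with null γ0 = γ1 = 0, that is, δ = 0 and θ = 0 together. The stated question is only γ1 − γ0 = θ = 0.
2. *0/1 product term.* The single coefficient φ is the GLP-1 RA log rate ratio within the LY3209590 arm, φ = δ + θ. The effect in the degludec arm is fixed at zero.

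*False signal.* Take rates of 0.5/year in non-users and 0.4/year in users, in both arms. The treatment rate ratio is 0.5/0.5 = 1 and 0.4/0.4 = 1, so θ = 0. But γ0 = γ1 = φ = ln(0.4/0.5) = −0.22, and both tests target a non-zero quantity.

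*Missed signal.* Take δ = ln 0.6 and θ = ln(1/0.6). The treatment rate ratio then differs 1.67-fold between subgroups, but φ = ln 0.6 + ln(1/0.6) = 0.

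**Simulation A, no true interaction.** From SAP Section 5: 888 randomized 1:1 (444 per arm), about half on GLP-1 RA balanced by arm, 15% dropout (taken as partial exposure). Assumed, because the documents give no values: negative binomial counts, base rate 0.25–1.0/year, dispersion 3–5, sulfonylurea use in 25% with rate ratio 2, no treatment effect. There were 2,004 replicates per setting, with likelihood-ratio tests at 0.05 and Monte Carlo SE at most √(0.25/2004) = 1.1 points.

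Rejection (%) at base rate 0.5/year, dispersion 3:

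| GLP-1 RA rate ratio (both arms) | 1.0 | 0.8 | 0.7 | 0.5 |
|---|---|---|---|---|
| As written, class coding, 2 df | 6.5 | 23.8 | 52.9 | 97.0 |
| As written, product term, LY3209590 arm | 7.1 | 18.6 | 36.9 | 84.4 |
| As written, product term, degludec arm | 5.3 | 17.3 | 37.4 | 83.7 |
| Main effect included, 1-df interaction | 6.6 | 5.9 | 5.7 | 5.3 |

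Other settings, 2-df test as written / 1-df test with main effect (%):

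| Base rate, dispersion | 1.0 | 0.8 | 0.7 | 0.5 |
|---|---|---|---|---|
| 0.25, 3 | 6.0 / 6.3 | 19.3 / 5.8 | 40.8 / 5.8 | 90.6 / 5.3 |
| 1.0, 3 | 6.6 / 6.4 | 30.3 / 6.3 | 62.7 / 6.0 | 99.5 / 5.4 |
| 0.5, 5 | 7.0 / 5.5 | 19.4 / 5.8 | 38.6 / 6.3 | 91.5 / 6.2 |

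Across these settings the product term rejects in 15–22% at rate ratio 0.8, 27–45% at 0.7 and 70–92% at 0.5.

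**Simulation B, coded separately.** It uses the same trial structure, with baseline HbA1c in the model and no sulfonylurea effect.

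- *0.5/year, dispersion 3, 500 replicates.* At GLP-1 RA rate ratios 1.0 / 0.8 / 0.6 the 2-df test rejects in 7.0 / 19.6 / 80.6%, the product term in 6.0 / 15.2 / 59.8%, and the 1-df test with main effect in 5.4 / 6.2 / 5.2%.
- *5/year, dispersion 2, 150 replicates.* At 0.8 / 0.6 the figures are 45.3 / 100%, 33.3 / 91.3% and 2.0 / 6.0%.
- *What the product term estimates.* Its exponentiated mean is 0.79–0.80 when the GLP-1 RA rate ratio is 0.8, and 0.60 when it is 0.6. It is recovering the GLP-1 RA effect, while the true interaction ratio is 1.
- *Missed signal.* With δ and θ as in that example, at 5/year and dispersion 2, the product term rejects in 5.3% of runs against 73.3% for the correct test.

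**The case against.** The best defense is that this is shorthand. GLP-1 RA use is a Yes/No stratification factor and the analyses run in SAS, so class coding is the natural reading. Under it the model fits the same four cell means with or without the listed main effect. The subgroup rate ratios and their ratio are unchanged, nothing estimated is biased, and a 1-df contrast can be extracted. The body-weight, insulin dose and CGM sentences also leave out a lower-order term (treatment by GLP-1 RA) that their 3-way term absorbs, so the section may not be meant as a literal design matrix. The stated purpose points to a single contrast, and the table specifications sit in documents not available here. The simulated sizes also depend on assumed rates and GLP-1 RA effects.

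Most of this is fair, and a drafting slip is the likely explanation. Two things remain. The SAP names neither the coding nor the contrast, while it does say interaction effects are judged at 0.05; under class coding, the test of the term it lists has 2 df and answers a different question. And the parallel model in 4.7.2.3, built on the same base regression, does list the subgroup factor. Shorthand therefore does not turn the written term into a valid interaction test.

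**Conclusion.** The concern holds: followed literally, the model does not answer the question in Protocol 9.3.7. A background-rate difference between GLP-1 RA users and non-users, equal in both arms, is enough to produce a reported interaction.

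The size depends on that difference. If GLP-1 RA use does not affect the rate, the term as written rejects in about 5–7% of trials, like the correct test. The higher rejection figures rest on assumed event rates, dispersion and GLP-1 RA rate ratios below 1, since the documents supply none of these.

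The consequences are bounded. The objective is tertiary, the test is unadjusted, and no primary or key secondary claim uses it. The separate analyses within each subpopulation remain valid and would show similar rate ratios beside a spurious interaction. The gap is confined to the participant-reported hypoglycemia rates. It should be corrected, but it does not threaten the trial's main conclusions.

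**What to change.** In SAP 4.7.2.1, list GLP-1 RA use at randomization as a factor alongside its interaction with treatment, as 4.7.2.3 does for its subgroups. The model then contains treatment, baseline HbA1c, GLP-1 RA use (Yes/No) and treatment by GLP-1 RA use, with the log-exposure offset. State that heterogeneity is judged by the 1-df test of the interaction.

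The cost is one sentence and one extra parameter relative to the product-term reading (none under class coding). It needs no new data and leaves the per-subpopulation analyses unchanged. Making the change before unblinding also removes a choice of coding and contrast that could otherwise be made with results in view.
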